4.5.2 Sputum Colour

Sputum colour is assessed by a standardised colour chart- patients are graded as mucoid (clear or grey phlegm, muco-purulent (light yellow or green) and purulent (dark yellow or green). We will present the number (%) of participants in each group who have had an exacerbation with a change in colour. We will also provide descriptive statistics for the proportion of exacerbations per person where a colour change is present.

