GSK	Glaxo SmithKline
HRCT	High-resolution computed tomography
ICF	Informed consent Form
ICH	International Conference on Harmonisation
ICS	Inhaled corticosteroid
IMP	Investigational Medicinal Product

ISF	Investigator Site File
ISRCTN	International Standard Randomised Controlled Trials Number
IVRS	Interactive Voice Response System
LABA	Long-acting beta agonist
LAMA	Long-acting muscarinic antagonist
LTOT	Long Term oxygen therapy
MHRA	Medicines and Healthcare products Regulatory Agency
NIMP	Non-Investigational Medicinal Product
PI	Principal Investigator
PIS	Patient Information Sheet
QA	Quality Assurance
REC	Research Ethics Committee
RN	Research Nurse
SAE	Serious Adverse Event
SAR	Serious Adverse Reaction
SDV	Source Data Verification
SPC	Summary of Product Characteristics
SOP	Standard Operating Procedure
SUSAR	Suspected Unexpected Serious Adverse Reaction
TMF	Trial Master File
TMG	Trial Management Group
TSC	Trial Steering Committee

TRIAL SUMMARY

Trial Title	THE MICROBIAL EFFECT OF INHALED STEROIDS IN SEVERE COPD PATIENTS WITH ASSOCIATED BRONCHIECTASIS
Study Acronym	TEMPESTAS
Clinical Phase	Phase 2b
Trial Design	Open Label Randomised Control Trial
Trial Participants	COPD patients with coexistent diagnoses of Bronchiectasis
Planned Number of Participants	80
Planned Number of Sites	3 – 6
Countries Anticipated to be Involved in Trial	UK
Treatment Duration	12 months
Follow up Duration	1 year
Total Planned Trial Duration	30 months
Primary Objective	To investigate the microbiological impact of inhaled corticosteroids over 1 year in patients with GOLD Stage D COPD and a co-diagnosis of bronchiectasis.
Secondary Objectives	Look at the effect of dual vs. triple therapies for all the endpoints mentioned.
Primary Endpoint	Baseline to 1-year change (expressed in log units) in colony forming units per ml between treatment arms (LABA-LAMA plus corticosteroid versus LABA-LAMA only)
Secondary Endpoint	Sputum colour, Sputum microbiota, Sputum bacterial load (>10 ⁶ CFU/ml), Spirometry, Patient symptoms, serum and sputum inflammation, exacerbations and mortality rate.
IMP(s)	Delivered via standard inhalers used routinely in COPD patients: dual bronchodilators (Umeclidinium and Vilanterol 55/22 mcg) vs. triple therapy (Fluticasone furoate, umeclidinium and vilanterol 92/55/22 mcg) both once a day
IMP Route of Administration	Inhaled products
NIMP(s)	Rescue Medication - Salbutamol 5mg/2.5 ml Nebuliser Solution

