2. STUDY OBJECTIVES

2.1 OBJECTIVES

2.1.1 Primary Objective

In patients with severe COPD and bronchiectasis, does the addition of inhaled corticosteroids:

- Alter the microbial load of pathogens?
 - o ICS beneficial effect would lead to an expected reduction in microbial load, with less significant bacterial loads (10 colony forming units/ml or more).
 - o ICS detrimental effect, would lead to an expected increased microbial load, with significant bacterial loads (10 colony forming units/ml or more)¹².

This would be assessed between the two groups (LABA-LAMA-ICS and LABA-LAMA arms).

2.1.2 Secondary Objectives (between two arms of the study) to assess if ICS:

- 1. Are beneficial, patients will have a broadened microbial diversity in sputum microbiata and if detrimental there would be loss of this diversity¹³⁻¹⁵.
- 2. Alter sputum colour, airways and systemic inflammation. The mechanism of inhaled corticosteroids is anti-inflammatory, and the hypothesis is that inhaled

corticosteroids might improve sputum colour and reduce sputum and serum inflammation¹².

- 3. Impact on microbial and mycobial community composition as explained in endpoints section 2.
- 4. Impact on spirometry (forced expired volume in 1 second, forced vital capacity, its ratio and mid expiratory flows FEF25-75).
- 5. Impact on health status using well-validated quality of life questionnaires in bronchiectasis (COPD Assessment Tool¹⁶ and St George's Respiratory Questionnaire¹⁷).
- 6. Moderate/ severe exacerbation rate and time to first moderate/ severe exacerbation.
- 7. Investigate if addition of inhaled corticosteroid has an overall beneficial/detrimental effect to the mortality rate and whether that correlates with the microbial diversity that we are also assessing in these 2 groups.

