2.2.2 Secondary Endpoints

- 1. Change in sputum microbial diversity and microbial biomass (see analyses below for details) ¹³⁻¹⁵ between the two arms.
- 2. **Sputum colour** as assessed by a standardised colour chart- patients are graded as mucoid (clear or grey phlegm, muco-purulent (light yellow or green) and purulent (dark yellow or green) ¹⁸.
- 3. **a) Microbial community composition** (gram negative/positive ratio, abundance of potential pathogens etc.)¹⁴
 - **b) Fungal microbiome**: between the two groups to see if ICS can influence the heterogeneity of the fungal community in terms of absolute and relative abundance.²⁰⁻²¹
- 4. **Spirometry**: forced expired volume in 1 second, forced vital capacity and its ratio and mid expiratory flows (FEF25-75) (attenuation of decline in lung function would be of long-term benefit to patients if found).
- 5. **Quality of Life**: quality of life assessed by the COPD Assessment Tool (CAT) ¹⁶ and St. George's Respiratory Questionnaire¹⁷. Breathlessness is included as part of this questionnaire.
- 6. **Sputum inflammation**: we will assess sputum myeloperoxidase as a measure of neutrophil burden and free elastase activity¹².
- 7. **Serum inflammation**: we will measure white cell count and differential, C Reactive Protein (CRP) and intercellular adhesion molecule 1 (ICAM-1)¹¹ Previous research has shown that at high bacterial loads there is increased ICAM-1¹²
- 8. **Exacerbations**: These would be categorised as
 - *time to the *first moderate or severe exacerbation* requiring treatment with antibiotics and/steroids, **number of exacerbations* (needing antibiotics and/steroids) over 12 months including hospitalisations

*number of participants with radiologically confirmed *pneumonia* over this period.

- 9. **Mortality rate** between the 2 arms of the study groups. Considering the group's overall but also separately broken down by microbe and microbial diversity.
- 10. Safety endpoints: The incidence of all AE and SAE across both treatment arms would be described as well as a safety endpoint. To assess and investigate safety and benefits of a trial design like this, we will also document parameters such as respiratory failure), hospitalised exacerbations (along with other exacerbation data as specified above), and trial dropout due to worsening COPD symptoms as safety endpoints. This would be documented between both the arms of the study.

[figure not shown]

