8. STATISTICS AND DATA ANALYSIS

8.1 SAMPLE SIZE CALCULATION

With a sample size of 36 per group we would be able to detect a difference of 0.76 log unit in the change in bacterial load between treatment arms assuming a common standard deviation of 0.98 log units based on a two-sided, two-sample test with 5% level of significance and 90% power¹⁹. A 10% drop out rate increases this to 80 patients (40 per group).

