4.5 Secondary Outcomes

4.5.1 Sputum

Table showing the number and percent of participants with a of clinically significant change in CFU at 12 months compared to baseline split by treatment allocation. Where a clinically significant change in CFU is defined as a difference of 1 log (CFU /ml). Comparisons between treatment allocation will be made using a binomial test for the comparison of proportions and accompanying this we will present the difference in proportion and 95% CI for the difference.

For each of the following markers we will perform a comparison between treatment arms for baseline to 1-year change will be analysed using a two-sample t-test. Descriptive statistics will be presented by treatment arm at each time point in addition to the baseline to 1-year change, and the pattern of change over time shall be presented graphically.

- Sputum microbial diversity although stipulated as an endpoint in the protocol this information is not available and will not be presented in the statistical analysis.
- Microbial biomass expressed as quantified by 16S rDNA pg/ml

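### The SAP never analyses graded sputum colour, and its 1-log CFU responder has no sign, so neither secondary output can show the improvement or harm the protocol describes

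*SAP*

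**What the plan says.** **Sputum colour.** Protocol 2.2.2, item 2, defines the endpoint "as assessed by a standardised colour chart- patients are graded as mucoid", muco-purulent or purulent. Protocol 2.1.2, item 2, gives the hypothesis: "corticosteroids might improve sputum colour and reduce sputum and serum" inflammation. Table 1 (protocol 5.3) has a sputum colour row ticked at baseline, month 6 and month 12. The table layout is damaged in the text available, and a further tick seems to fall at the last follow-up visit.

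SAP 4.5.2 repeats the three grades and then specifies two outputs. One is: "We will present the number (%) of participants in each group who have had an exacerbation with a change in colour". The other is a descriptive summary, per person, of the share of exacerbations with a colour change. It specifies no grade by visit, no change from baseline and no comparison between arms.

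**CFU responder.** SAP 4.5.1 compares the proportion of participants with a clinically significant change at 12 months, using a test of two proportions and a 95% CI. The definition is: "Where a clinically significant change in CFU is defined as a difference of 1 log (CFU /ml"). No sign is given. Protocol 2.1.1 reads a lower microbial load as benefit and a higher one as harm.

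**Load threshold.** The Trial Summary's secondary endpoints begin "Sputum colour, Sputum microbiota, Sputum bacterial load", the last with a threshold of more than 10^6 CFU/ml. Neither protocol 2.2.2 nor any SAP analysis takes up that threshold.

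**The concern.** The colour objective asks whether the grade improves. The SAP's outputs concern exacerbations instead, which are a separate post-randomisation outcome (protocol 2.2.2, item 8). An arm with fewer exacerbations has fewer chances to record a colour change even if colour is unaffected. The exacerbation data listed in protocol 6.5 include a change in colour but no grade or direction, so the summaries cannot distinguish better from worse.

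The CFU responder is formally tested. If rises and falls are pooled, a significant difference cannot be read as good or bad, and a real shift can leave no difference at all. If the sign is instead settled at analysis, it is settled after the data exist, in an open-label trial.

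**Working it through.** **Inputs** (protocol 8.1): "With a sample size of 36 per group we would be able to detect a difference of 0.76 log unit", "assuming a common standard deviation of 0.98 log units", and a "two-sided, two-sample test with 5% level of significance and 90% power".

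**The plan's own figure.** The normal approximation gives n = 2(1.960 + 1.282)² × 0.98² / 0.76² = 34.9, so 35 per arm. The t-based calculation gives 35.93, so 36 per arm, with power 0.901. Then 36 / 0.9 = 40 per arm, 80 in total. The stated sample size reproduces.

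**CFU responder.** Assumptions: the 12-month change is normal with SD 0.98 in each arm; the 1-log threshold is in the same log units; a change of exactly 1 counts. For an arm with mean change m:

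- rise: P(X ≥ 1) = 1 − Φ((1 − m)/0.98)
- fall: P(X ≤ −1) = Φ((−1 − m)/0.98)
- unsigned: the sum of the two

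For m = 0: 0.154 + 0.154 = 0.308. For m = +0.76: 0.403 + 0.036 = 0.440 (from unrounded terms). For m = −0.76 the two terms swap and the sum is again 0.440. For m = ±0.38: 0.263 + 0.080 = 0.343.

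Power at n = 36 per arm is Φ((|p1 − p2| − 1.96·s0)/s1), with s0 = √(2·p̄(1 − p̄)/n), p̄ the mean of the two proportions, and s1 = √((p1(1 − p1) + p2(1 − p2))/n). Example, rises in the first row below: |p1 − p2| = 0.250, s0 = 0.106, s1 = 0.102, power 66.2%.

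The documents do not give the arm means, so several pairs that are 0.76 apart are shown:

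| Mean change, dual / triple | Unsigned, dual v triple | Power | In direction of triple's shift from dual | Power |
|---|---|---|---|---|
| 0 / +0.76 | 30.8% v 44.0% | 20.9% | rise 15.4% v 40.3% | 66.2% |
| 0 / −0.76 | 30.8% v 44.0% | 20.9% | fall 15.4% v 40.3% | 66.2% |
| −0.38 / +0.38 | 34.3% v 34.3% | 5% (no difference) | rise 8.0% v 26.3% | 54.5% |
| −0.20 / +0.56 | 31.8% v 38.2% | 8.3% | rise 11.0% v 32.7% | 60.7% |
| +0.38 / +1.14 | 34.3% v 57.1% | 49.3% | rise 26.3% v 55.7% | 72.5% |

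The first two rows are opposite conclusions with identical unsigned results. Exact enumeration of the pooled z-test agrees within about 1 percentage point for the unsigned counts and within 5 for the directional ones.

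**Sputum colour.** The plan has no figure to recompute. The mechanism can be illustrated only with assumed inputs. Suppose exacerbations are Poisson at rate λ per year and half show a colour change in both arms. Then P(at least one colour-change exacerbation) = 1 − exp(−λ/2):

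- λ = 2.0 v 1.5: 63% v 53%
- λ = 1.0 v 0.75: 39% v 31%

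These gaps arise from exacerbation frequency alone. People with no exacerbation, exp(−λ), have no value for the per-person proportion: 37% at λ = 1 and 14% at λ = 2.

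**The case against.** Much of the case on the other side stands.

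- **The sign is unstated, not excluded.** A reader might infer that the SAP has chosen to count absolute changes. It does not say so. SAP 4.4 defines change as 12 months minus baseline, and 4.5.1 speaks of 12 months compared with baseline. The defect is silence, and a phrase would cure it.
- **Direction is not lost to the trial.** A reader might infer that the trial cannot tell benefit from harm on bacterial load. The primary t-test uses the signed change, with descriptive statistics by visit and a plot.
- **The first colour count is not a selected subgroup.** A reader might infer that the whole colour analysis is restricted to people who exacerbate. The first output is a percentage of participants in each arm. Only the per-person proportion needs an exacerbation. Both are already descriptive.
- **The 1-log responder is not in protocol 2.2.2.** Protocol 8.2 mentions a clinically significant CFU change only as an example of a binary response. The SAP nonetheless lists and tests it among the secondary outcomes.
- **Capture of the visit grade is not certain.** Table 1 schedules colour, but the eCRF lists for Visits 2, 4 and 5 (protocol 6.2 to 6.4) mention only sputum collection. One cannot assume that the grades are in the database.
- **General rules might cover colour.** SAP section 2 promises counts and percentages for categorical data and descriptive statistics for markers at each time point. SAP 4.5.2, which is specific to colour, does not apply this, whereas 4.5.4 to 4.5.7 set it out for their own markers.
- **Covariate adjustment is not planned.** Both documents say so, which argues for a simple comparison rather than an adjusted model as the default.

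**Conclusion.** The point holds in a limited form. The SAP contains no specific analysis of the graded colour endpoint, and what it reports instead cannot show the hypothesised improvement. Exacerbation colour carries some information, but without grade or direction and, in the first count, mixed with how often people exacerbate.

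As written, the 1-log responder gives the same answer for a 0.76-log benefit and a 0.76-log harm from a dual-arm mean of 0. Over the arm means tried, its power is 5% to 49%, against 54.5% to 72.5% for a count in the direction of the shift. The 5% belongs to the exactly symmetric case and is the extreme, not the expectation. All these figures rest on normal changes with SD 0.98 and on arm means that the documents do not give. The colour percentages are illustrations from assumed rates and no estimate of bias in this trial.

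The primary analysis is unaffected. This is a gap in the secondary analyses that should be closed before the data are analysed.

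**What to change.** **SAP 4.5.2.** First confirm that the eCRF holds the colour grade from scheduled visits. If it does, tabulate the three grades by arm at baseline, 6 and 12 months, add a baseline-to-12-month shift table, and make one simple ordinal comparison at 12 months, for example a Wilcoxon rank-sum test. A proportional-odds model with baseline grade is optional and would need an explicit exception to the no-covariate statement. Keep the exacerbation colour summaries as supportive. If the grade was not captured, say so in the SAP, as it already does for other unavailable endpoints.

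**SAP 4.5.1.** Replace the single responder with two: a rise of at least 1 log10 and a fall of at least 1 log10, each with the difference in proportions and its 95% CI. State the log base.

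**Load threshold.** Add the proportion above 10^6 CFU/ml at 12 months by arm, or reconcile the Trial Summary with protocol 2.2.2 and the SAP.

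**Cost.** SAP wording, a few tables and one more secondary comparison from splitting the responder, besides the colour comparison and, if added, the threshold proportion. Table 1 already schedules colour and quantitative microbiology, so no new visit or assay is needed, provided the colour grade was recorded.

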4.5.3 Sputum composition

Microbial community composition – *this will be conducted by the laboratory and will not form part of the statistical analysis.*

Fungal microbiome – although stipulated as an endpoint in the protocol this information is not available and will not be presented in the statistical analysis.

4.5.4 Spirometry

For each of the following markers we will perform a comparison between treatment arms for baseline to 1-year change will be analysed using a two-sample t-test. Descriptive statistics will be presented by treatment arm at each time point in addition to the baseline to 1-year change, and the pattern of change over time shall be presented graphically.

- FEV₁
- FVC
- FEV₁ / FVC ratio
- Mid-expiratory flows FEF25/75

Version No 2.1

Effective Date 27Jun2025

4.5.5 Quality of life

For each of the following markers we will perform a comparison between treatment arms for baseline to 1-year change will be analysed using a two-sample t-test. Descriptive statistics will be presented by treatment arm at each time point in addition to the baseline to 1-year change, and the pattern of change over time shall be presented graphically.

- SGRQ-C total score
- SGRQ-C symptom score
- SGRQ-C activity score
- SGRQ-C impact score
- CAT total score

4.5.6 Sputum inflammation

For each of the following markers we will perform a comparison between treatment arms for baseline to 1-year change will be analysed using a two-sample t-test. Descriptive statistics will be presented by treatment arm at each time point in addition to the baseline to 1-year change, and the pattern of change over time shall be presented graphically.

- sputum myeloperoxidase
- free elastase activity

4.5.7 Serum inflammation

For each of the following markers we will perform a comparison between treatment arms for baseline to 1-year change will be analysed using a two-sample t-test. Descriptive statistics will be presented by treatment arm at each time point in addition to the baseline to 1-year change, and the pattern of change over time shall be presented graphically.

- white cell count
- eosinophil
- neutrophil
- monocyte
- lymphocyte
- erythrocyte sedimentation rate (ESR)
- C Reactive Protein (CRP)
- intercellular adhesion molecule 1 (ICAM-1)

4.5.8 Exacerbations

Table showing the number and percent of participants with radiologically confirmed pneumonia split by treatment allocation.

Descriptive analysis split by treatment allocation, of:

- number of exacerbations requiring treatment with antibiotics and or steroids
- number of exacerbations requiring treatment with antibiotics and or steroids that also includes hospitalisation

A Kaplan-Meier survival curve stratified by treatment allocation will be presented along with the accompanying log-rank statistic for the time to first moderate or severe exacerbation where this is defined as an exacerbation requiring treatment with antibiotics and or steroids.

Version No 2.1

Effective Date 27Jun2025

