3.12.2 Lost to follow up

If a subject fails to attend the clinic for a required study visit, the site should attempt to contact the subject and re-schedule the missed visit as soon as possible. The site should also counsel the subject on the importance of maintaining the assigned visit schedule and confirm whether or not the subject wishes to and/or should continue in the study based on previous noncompliance. In cases where the subject does not return for the rescheduled visit or cannot be reached to reschedule the missed visit, the site should make every effort to regain contact with the subject (3 telephone calls and if necessary, a certified letter to the subject's last known mailing address) so that they can appropriately be withdrawn from the study. These contact attempts should be documented in the subject's medical record. If the subject continues to be unreachable, only then will he/she be considered to have withdrawn from the study with a primary reason of "Lost to Follow-up". For all other subjects withdrawing from the study, an alternative reason for discontinuation should be recorded in the eCRF. Every effort should be made to collect survival status (whether the subject is still alive).

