4.5.9 Mortality rate

Table showing number and percentage of participants who died during the follow-up period split by treatment allocation.

A Kaplan-Meier survival curve stratified by treatment allocation will be presented along with the accompanying log-rank statistic for the time from baseline to death or censor (this will either be the date of 12 month visit or date of withdrawal if withdrawn prior to completion).

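### Exacerbation counts, including hospitalised ones, are summarised by arm with no person-time, rate ratio or confidence interval, although the protocol objective is a rate and follow-up length varies

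*SAP*

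**What the plan says.** **Exacerbations.** Protocol 2.1.2, item 6, sets the objective: "Moderate/ severe exacerbation rate and time to first moderate/ severe exacerbation". Protocol 2.2.2, item 8, words the matching endpoint as a number over 12 months, hospitalisations included. Item 10 also lists hospitalised exacerbations as a safety endpoint, beside respiratory failure and dropout from worsening COPD.

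SAP 4.5.8 gives a "Descriptive analysis split by treatment allocation, of" two counts: treated exacerbations, and treated exacerbations that involved hospitalisation. Time to first moderate or severe exacerbation gets Kaplan-Meier curves and a log-rank statistic. SAP 4.5.10 gives respiratory failure and COPD-related dropout a binomial test, a difference and a 95% CI, but refers hospitalised exacerbations back to 4.5.8.

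**Pneumonia.** SAP 4.5.8: "Table showing the number and percent of participants with radiologically confirmed pneumonia split by treatment allocation". Protocol 8.2, repeated in SAP section 2, has a general rule that binary responses get a binomial test, a difference in proportions and a 95% CI.

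**Deaths.** SAP 4.5.9 plans a number and percentage by arm, and a Kaplan-Meier and log-rank analysis of time to death or censoring. On the censoring date it says "this will either be the date of 12 month visit or date of withdrawal if withdrawn prior to completion". Protocol 3.12.2, on participants lost to follow-up, says "Every effort should be made to collect survival status (whether the subject is still alive".

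**Length of follow-up.** Under Protocol 3.12.1, a participant who stops study medication has the final visit brought forward, and one who leaves entirely contributes only data collected up to that point. SAP 3.1 analyses participants as randomised. SAP 3.4 plans no imputation.

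**The concern.** A count is comparable between arms only if the arms were observed for the same time. Here observation time depends on when a participant stops, and the trial is open label, with COPD-related dropout itself a safety endpoint. A participant who leaves at month 2 without an exacerbation enters the summary exactly like one followed for 12 months without one, so the arm with more early exits tends to show fewer exacerbations.

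The summary also gives no ratio or interval, so the reader cannot see which differences the data exclude. Hospitalised exacerbations are the clearest case: of the three safety endpoints in Protocol 2.2.2, item 10, that the SAP treats together, this one alone ends with no between-arm estimate, and no reason is given.

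Two related gaps are smaller. Pneumonia, which Protocol 1.1 calls the main reported risk of ICS in COPD, is shown as number and percent without the interval that the plan's general rule would supply. For deaths, the plan does not say what happens to one that is known but occurred after withdrawal.

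**Working it through.** **1. The plan's own figure.** Protocol 8.1 states "With a sample size of 36 per group we would be able to detect a difference of 0.76 log unit", "assuming a common standard deviation of 0.98 log units", and "based on a two-sided, two-sample test with 5% level of significance and 90% power". The normal approximation gives n = 2 × (1.960 + 1.282)² × 0.98² / 0.76² = 34.9, so 35 per arm. With the noncentral t distribution, power is 0.892 at 35 and 0.901 at 36, so 36 is right. Then 36 / 0.90 = 40 per arm, 80 in total. The figure reproduces. It concerns bacterial load only; neither document gives a precision or power figure for exacerbations, pneumonia or death. The 10% dropout is overall, with no split by arm, so everything below rests on stated assumptions.

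**2. Distortion of the crude count ratio.** Assume leavers go at 6 months. Mean follow-up in an arm with exit proportion d is 1 − 0.5d years. The crude ratio of mean counts is the true rate ratio times the ratio of mean follow-up.

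| Exit, dual / triple | Mean follow-up, dual / triple (years) | Crude ratio if true ratio is 1.00 | Crude ratio if true ratio is 0.75 |
|---|---|---|---|
| 10% / 10% | 0.950 / 0.950 | 1.00 | 0.75 |
| 20% / 10% | 0.900 / 0.950 | 1.06 | 0.79 |
| 20% / 5% | 0.900 / 0.975 | 1.08 | 0.81 |
| 30% / 10% | 0.850 / 0.950 | 1.12 | 0.84 |

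If exit is heavier in the triple arm, the ratio moves the other way (0.900 / 0.950 = 0.95; 0.850 / 0.950 = 0.89). A log follow-up-time offset removes this when leaving is unrelated to exacerbation risk.

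**3. What a rate ratio would deliver.** With 40 per arm, rate λ per year, mean follow-up 0.95 years and dispersion k, SE(log RR) = √[2 × (1/(40 × λ × 0.95) + k/40)], and the 95% CI multiplies and divides the ratio by exp(1.96 × SE).
- λ = 2, k = 0.5: SE = √[2 × (1/76 + 0.0125)] = 0.227, factor 1.56.
- λ = 2, k = 1: factor 1.72.
- Over λ from 1 to 3 and k from 0 to 1: factor 1.30 to 1.87.

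**4. Pneumonia.** The risk table in Protocol 4.5 reports 3% with vilanterol alone and 6% to 7% with fluticasone furoate/vilanterol. With 40 per arm that is 1.2 versus 2.4 to 2.8 participants. The Wald half-width for 3% versus 6% is 1.96 × √(0.03 × 0.97/40 + 0.06 × 0.94/40) = 9.1 points; for 3% versus 7% it is 9.5 points. Power is 9% to 13%.

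**5. Deaths.** Assume a true 1-year risk of 10% at constant hazard, with leavers going at 6 months.
- *Non-informative leaving.* The crude percentage is (1 − d) × 0.10 + d × (1 − 0.9^0.5), where 1 − 0.9^0.5 = 0.0513. It is 9.5%, 9.0% and 8.5% for d = 10%, 20% and 30%. Kaplan-Meier gives 10% each time.
- *Informative leaving.* Let 20% leave, with hazard m times higher afterwards. The true risk is 0.8 × 0.10 + 0.2 × (1 − 0.9^0.5 × 0.9^(0.5m)), which is 0.109 (about 11%) for m = 2 and 0.126 for m = 4. Kaplan-Meier with censoring at withdrawal stays near 10%, and the crude figure at 9.0%. In an arm of 40, the deaths missed by the crude table are 40 × (0.109 − 0.090) = 0.8 to 40 × (0.126 − 0.090) = 1.4.

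**The case against.** The case on the other side has real weight.

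- *SAP 4.5.8 follows the protocol's endpoint.* Protocol 2.2.2 speaks of a number, so the mismatch with the rate in 2.1.2 lies within the protocol. That is fair, but a number over 12 months is well defined only for those observed for 12 months.
- *A comparison using follow-up time already exists.* The log-rank test for time to first exacerbation is one. A reader might infer that exacerbations get no valid comparison between arms; that goes too far. What remains is that the test has no effect size, ignores repeat events and does not address hospitalised exacerbations.
- *Pneumonia is arguably covered.* A reader might infer that no comparison is planned. The general binary rule can be read to include pneumonia; the gap is that 4.5.8 does not carry it through, whereas 4.5.1 and 4.5.10 restate it for other outcomes.
- *Censoring does not make leavers event-free.* A reader might infer that the mortality curve treats early leavers as survivors. It does not: censoring removes them from the risk set, and step 5 shows no bias when leaving is non-informative.
- *SAP 4.5.9 does not exclude later deaths.* A reader might infer that deaths after withdrawal are discarded by rule. The text can be read as fixing the censoring date only for people with no recorded death. It is silent, so this is an ambiguity to settle.
- *Unequal exit would be visible.* SAP 3.4 and 4.7 report withdrawals by arm, and 4.5.10 compares COPD-related dropout. That would alert a reader but would not correct the counts.

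**Conclusion.** The point holds for exacerbation counts. SAP 4.5.8 gives neither a rate nor a between-arm estimate for an objective worded as a rate, and hospitalised exacerbations lose the comparison given to the other two safety endpoints handled in 4.5.10.

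The distortion from ignoring follow-up time is nil at equal 10% exit and about 6% to 12% in the unequal scenarios in the table. Those splits and the 6-month exit time are assumptions; the documents give no exit figures by arm. The distortion is also small beside the likely interval (ratio multiplied and divided by 1.30 to 1.87). The main loss is therefore the missing estimate and interval, with bias second.

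Pneumonia needs a drafting repair. With about 1 to 3 expected cases per arm, the interval cannot settle safety, but it would stop a bare percentage being read as reassurance. For deaths, the exposure is possible informative censoring and the possible loss of known deaths, about one per arm in the assumed scenario. That leaving is related to risk of death is plausible, but nothing in the documents establishes it.

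All of these are secondary endpoints of a proof-of-concept trial. The primary analysis is untouched.

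**What to change.** Amend the SAP before database lock.

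- **4.5.8, exacerbations.** Add a negative binomial model (or Poisson with robust standard errors) for moderate or severe exacerbations, with log follow-up time as offset. Report the rate ratio and 95% CI. Do the same for hospitalised exacerbations if counts allow; otherwise report events and person-years by arm. Define follow-up time as randomisation to the last contact at which exacerbations were ascertained, up to 12 months. The model can be unadjusted, which keeps to the stated plan of no covariates.
- **4.5.8, pneumonia.** State that the general binary rule applies: difference in proportions with a 95% CI, preferably score-based because so few cases are expected.
- **4.5.9, deaths.** Count all deaths known to have occurred within 12 months of randomisation, by allocated arm, including those after withdrawal or loss to follow-up where survival status is held. Censor everyone else at the last date known alive, up to 12 months. Protocol 3.12.1 restricts full withdrawals to data already collected, so state that this applies within consent limits.

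The cost is a few sentences of SAP text and one or two short models. Visit and change-of-status dates are already used in SAP 4.2, and Protocol 3.12.2 already asks sites for survival status after loss to follow-up. No new data collection is needed.
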